#### **Range of imposed performance variations (part B) – Sit to stand**

A STS seat height range definition procedure will permit the quantification of the appropriate personalized range of experimentally-induced performance variations for every participant. The 30CST requires the maximal frequency of STS transitions to be produced by the subjects on a standardized chair (fixed seat height of 43.2 cm), exposing them to incremental challenges due to physical exertion over a short time. In our study the baseline seat height will be normalized on the physical characteristic of the participants (=100% of the distance from the ground to the inferior margin of the patellar bone, measured in sitting, including the height of the shoes sole, wearing the same shoes as in all the other experimental parts and after ensuring vertical alignment of the tibia). The STS seat height range that will be used as personalized range of experimentally-imposed

performance variations (in Part B) will be then calculated as: baseline seat height  $\pm$  20% (from comfortable to lowest seat height, see 'verbal descriptors' below).

#### **Familiarization with perceptive task for Part B – 'Perception of imposed performance variations'**

At this point the experimenter will present two vertical visual scale on a screen, ranging from 0 to +100 or from 0 to -100, which have been designed to match the participants' perception of ongoing motor performance, either for treadmill walking or STS.

Verbal descriptors will be positioned on the right side of the scale at every 10th step describing different levels of walking speed or STS difficulty level. Note (see below) that the verbal descriptors of the two visual scales will be inversely directed, but that 'minimal seat height' represent the most difficult condition in the STS task and therefore correctly occupies the upper limit of the scale.

Perceived treadmill speed scale 0% =your comfortable speed; +100% =your maximal speed

Perceived seat-height scale 0% =your comfortable seat height; -100% = your minimal seat height

### **Experimental design Part A: 'Perception of self-paced performance variations'**

During Part A the participants will perform the experimental tasks (first the 6 minutes of walking and then the STS repetitions) of perceptive detection twice, with different instructions driving their attention on their performance quantity- or quality- variations: the order of the participant's execution of the two pair of experimental tasks will be counterbalanced at group level to mitigate any potential bias or effects that might arise from the order in which the tasks and relative instructions are presented.

#### **Task 1: Perceptive accuracy for walking speed variations during overground 6MWT**

The participants will be tested overground, during a 6MWT, for their ability of accurately perceive changes in their self-paced gait speed: they will be instructed to walk for 6 minutes at the maximal speed that they can maintain safely and reporting any perceived oscillation in their own speed by squeezing the handheld sensor. The reason for the selected modality to acquire patient reports is that holding the sensor in the hand can serve as a reminder for the ongoing perceptive task, ensuring a continuous attention toward their speed and acquisition of reports (the action of holding the sensor, without squeezing it, confirms that the participant is not perceiving any change in speed, accordingly to the received standardized instructions).

Neutral instructions will be provided to the subject before starting the 6MWT by reading the following script: "When you will hear the beep tone, squeeze the sensor and start walking at the maximal speed that you can maintain safely for the 6 minutes-length of the experiment. During this period, but only for the straight parts of the walking track, please pay attention to your walking speed. Natural variations in your walking speed may occur during the test. We want you to notice, and report them using the handheld sensor being them accelerations or decelerations, this information does not matter for our test and therefore you will not have to indicate it: as soon as you perceive a change in your walking speed, squeeze the sensor in your hand to save your report. Report only changes in speed that you perceived during the straight parts of the walking tract: all the

variations that are due to the turning will be cut out from the analysis. If you will squeeze during a turn, that report will be saved as if it was given three steps before the turn.

Participants will be also equipped with noise-cancelling headphones to avoid auditory perception of steps rhythm and influence of possible environmental distractions. Using wearable sensors to detect motor performance (spatiotemporal and kinematic parameter detected with a configuration of 6 OPALS – technology© IMU sensors: 2 over the dorsal part of the feet, 2 on the lower legs, 1 anterior to the sternum and 1 posterior to the third/fourth lumbar vertebra, see figure 4) will allow us to then compare the time and frequency of the reports with the actual speed variations, cutting out the steps executed while turning, and propose novel outcome measures: the change in speed at the first report as a perceptive threshold for overground walking speed changes, informing on the minimal clinically important change, and the ratio between reporting frequency and actual speed variability, reflecting perceptive accuracy (see example plot in Figure 6).

[figure not shown]

Figure 6 Perceptive accuracy for walking speed variations during overground 6MWT: Task 1 illustration, wearables placement and Perception vs Performance plot graphic illustration

The intensity of perceived fatigue will be asked just before and immediately after the test using the VAS-F (see Figure 4). Furthermore, a short structured interview will follow including the following question: "On a scale from 0 to 100, how certain are you that you have been precise/accurate in detecting ongoing variations in your performance? Please mark your confidence level on the presented visual scale". This question is then followed by an open-ended question where the participant is asked to report on which sensory information he/she was relying to gauge performance variations and give the reports: "On which aspects of your motor performance where you paying attention to detect variations and decide to give a report during the task? Please list them here".

[figure not shown]

Figure 7 Visual scale for confidence rating: subjective beliefs on their perceptive accuracy

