#### 6.4 Rate of Perceived Stability \*

Afterwards, the participants will perform the 6 Minute Walk Test (6MWT), walking back and forth in a 30m corridor as fast and safe as possible for 6 minutes, the 30 seconds Chair Stand Test (30CST), repeating STS transitions as fast and safe as possible for 30 seconds, and the Dual Joint Position Test (DJPT), a test for proprioception. (25)

Except for the T25FW, the participant will wear wearable sensors in pre-defined body positions for the gait and STS tests (6 OPALs – APDM technology© IMU sensors: 2 over the dorsal part of the feet, 2 on the lower legs, 1 anterior to the sternum and 1 posterior to the third/fourth lumbar vertebra; 1 Polar H10 chest-band for real-time heart rate monitor).

Figure 4 Wearable sensors placement on the body and working prototype of the force sensing device for perceptive tasks

The perceived fatigue will be asked just before and immediately after the 6MWT and the 30CST using the VAS-F, a 0-10 visual analogical scale for state fatigue.

Figure 5 10 points visual analogic scale for fatigue (VAS-F)

- **Familiarization with motor and perceptive tasks**

At this point the participant will be familiarized with the experimental procedures and the experimenter is defining the ranges of performance variations that will be experimentally-induced in part B. This will happen in the presented order:

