## Data and statistical analysis

Motor performance data (gait and STS kinematic, kinetics and spatial-temporal parameters) will be acquired by wearable sensors and extracted from Moveo software (APDM) as .csv file or raw data, and Matlab scripts will be used in case of parameters requiring specific calculation. Data acquired from the participants reports on their perception, during the experimental tasks in Part A and Part B, will be extracted with dedicated Matlab scripts. Statistical analysis will be performed using SPSS (V. 28.01). Tests of normality (Shapiro-Wilk test) will be used to determine if parametric or non-parametric statistical tests have to be used for the comparisons and correlations. The  $\alpha$  for all analyses will be set at 0,05.

**Clinical assessment** outcomes, with a particular focus on the MAIA-2, ISAQ and PAS scores and subscores, will be compared between groups with an independent T test (or with its non-parametric equivalent Mann-Whitney U-Test), to detect significant differences in the subjective beliefs about perceptive abilities.

In the **experimental Part A** we will obtain the participants' minimal perceptive threshold for self-paced performance variations which will be compared between groups with an independent T test (or with its non-parametric equivalent). We will also relate the frequency of the reports with the measured performance variability (coefficient of variation of the selected motor performance parameter: gait speed or STS duration) to obtain a novel outcome measure reflecting perceptive accuracy. We will study it between and within groups using a mixed model ANOVA with time and group as factors to detect significant differences between PwMS and controls and its variations relative to the accumulation of fatigue during the prolonged motor tasks. To investigate its interference with perceptive accuracy the difference between the subjective rate of fatigue (VAS-F) pre-post task protocols will be included in the analysis as covariate.

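### Part A walking: the stated rule removes only turning steps and sets no margin around turns or at the start, so braking, re-acceleration and start-up can enter the speed CV used in the accuracy ratio

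*Combined protocol and SAP*

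**What the plan says.** All references are to the combined protocol and SAP.

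- **Processing rule.** Part A, Task 1 (overground 6MWT), in the paragraph on wearable sensors, compares reports with actual speed after "cutting out the steps executed while turning, and propose novel outcome measures". No buffer before or after the turn is given.
- **Participant script.** The same section tells participants that all "variations that are due to the turning will be cut out from the analysis". The smoothness script, under the repetition of Tasks 1 and 2 with adapted instructions, says the same. Neither script says how such variation is to be identified.
- **Squeezes in a turn.** "If you will squeeze during a turn, that report will be saved as if it was given three steps before the turn". This relocates a report. It removes no steps from the speed series.
- **Start.** "When you will hear the beep tone, squeeze the sensor and start walking at the maximal speed". No section drops the first steps.
- **Outcomes.** Task 1 defines "the ratio between reporting frequency and actual speed variability, reflecting perceptive accuracy" and "the change in speed at the first report as a perceptive threshold for overground walking speed changes". *Data and statistical analysis* gives the variability as the "coefficient of variation of the selected motor performance parameter: gait speed or STS duration", without saying which steps enter it. The accuracy outcome then goes into a mixed ANOVA with time and group as factors.
- **Track.** The clinical 6MWT, under *Cognitive and motor performance assessments*, is done "walking back and forth in a 30m corridor". The Part A walk gives no track length of its own.

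**The concern.** A walker slows on the straight before a turn and regains speed on the straight after it. These changes are caused by the turn but fall on steps that are not turning steps. The processing rule leaves them in the speed series, while the script tells participants that turn-related variation will not count. Such variance raises the CV without a matching expectation that it be reported, so the ratio falls for a reason that is not perception. Start-up steps raise the CV too, although for a different reason: no rule mentions them at all.

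If turning or starting behaviour differs between people with MS and controls, part of a group difference in the ratio would be a motor difference read as a perceptual one. The change in speed at the first report is exposed to the same problem if that report falls near a turn or the start.

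**Working it through.** The documents state no CV, ratio or effect size on this point, so there is no planned figure to reproduce. The calculation below shows only how sensitive the ratio is.

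**Assumed inputs (none from the documents unless stated).** 30 m per length (stated for the clinical 6MWT, assumed for Part A). 40 straight steps per length once turning steps are cut. On each side of the turn, three steps at 1/3, 2/3 and the whole of a dip of depth *d*. True straight-line CV *c*. The ratio is taken as reporting frequency divided by CV. The small fall in mean speed is ignored.

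**Turn transients.** In percentage points of speed:

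- Mean shift = 2(1/3 + 2/3 + 1)*d*/40 = 0.1*d*
- Mean square = 2(1/9 + 4/9 + 1)*d*²/40 = 0.0778*d*²
- Added variance = 0.0778*d*² − 0.01*d*² = 0.0678*d*²
- *d* = 5: 1.69. *d* = 20: 27.1
- Computed CV = √(*c*² + added variance); ratio falls by 1 − *c*/CV

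| True CV | CV, 5% dip | Ratio lower by | CV, 20% dip | Ratio lower by |
|---|---|---|---|---|
| 2% | √5.69 = 2.4% | 16% | √31.1 = 5.6% | 64% |
| 3% | √10.69 = 3.3% | 8% | √36.1 = 6.0% | 50% |
| 4% | √17.69 = 4.2% | 5% | √43.1 = 6.6% | 39% |

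A gentler ramp (1/4, 1/2 and 3/4 of the dip) adds variance 0.95 to 15.25. At true CV 3% the ratio is then 5% to 39% lower.

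**Start-up.** Assume the first three steps are 60%, 30% and 10% below steady speed, in a bin of 110 steps (about one minute). Added variance = (3600 + 900 + 100)/110 − (100/110)² = 41. With true CV 3% and no turn dips, the bin's CV is √(9 + 41) = 7.1%.

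The fair comparison is with later bins that also contain turns:

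- 20% dip: first bin √(9 + 41 + 27.1) = 8.8% against 6.0% later, a ratio about 32% lower
- 5% dip: first bin √(9 + 41 + 1.7) = 7.2% against 3.3% later, about 55% lower

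These apply only if time is binned by the minute, which Part A does not state.

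**Separate simulation.** A simulated six-minute walk at 1.5 m/s with 0.70 m steps, true CV 3%, two braking and two accelerating steps per turn (30% dip) and a three-step start gave a CV of 6.0% with these steps kept and 3.0% without. The start alone gave 3.9%; the turn-adjacent steps alone gave 5.5%. Across all its assumed inputs (1.2-1.9 m/s, true CV 2-5%, nought to three transitional steps, 30-50% dip), inflation ran from 1.11-fold (start only) to 4.41-fold.

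**The case against.** The strongest reply is that the script already promises to remove all turn-related variation, and that the phrase about turning steps is a short clause in a task description, not an algorithm. Extraction is left to Moveo and Matlab scripts, which may trim adequately. This stands in part. A reader might infer that the plan definitely keeps braking and accelerating steps, but the documents do not show that. They give two rules of different scope and make neither operational for these steps.

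Four further inferences go beyond the text.

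- **That participants were told to ignore the start.** They were not. Accelerations on the straight are literally reportable, and turning is the only stated exception. The start is an unaddressed transient, not a broken promise.
- **That a false time effect of a known size will follow.** *Data and statistical analysis* names time as a factor for Part A without a bin length; minute-by-minute analysis is described for Part B only. Comparing the 7.1% start-up CV with a clean 3% (a 58% fall) also overstates the contrast, because later bins contain turns too.
- **That these are the largest speed changes in the walk.** Nothing in the documents establishes this.
- **That the bias runs in a known direction.** The introduction supports slower walking and altered gait in MS, but says nothing specific about braking or starting.

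The study also calls itself exploratory, which lowers the stakes. It does not remove the need for a defined step selection, since this ratio carries the Part A walking comparison.

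**Conclusion.** The point holds as a cheap improvement. The processing rule is narrower than the promise made to participants, no margin closes the gap, and the start is not handled anywhere. If the stated rule is followed literally, turn and start transients enter the CV and lower the ratio for non-perceptual reasons. At true CV 3% the illustrated fall is 8-50%. The width of that range comes from the assumed dip, and the step count, ramp and CV are assumed as well. Start-up steps would further lower the ratio of whichever time bin contains them. Whether groups are affected differently, and in which direction, cannot be determined from the documents.

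**What to change.** Before analysis, state in *Data and statistical analysis*:

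1. One fixed number of steps (or distance) dropped before and after every turn, plus a fixed number of start-up steps, identical for all participants and applied to both the speed and smoothness series.
2. The same window for reports. Either exclude reports that fall inside it, or assign squeezes made in a turn to the last retained straight step. Count reporting frequency over the retained data, so that numerator, denominator and the change in speed at first report share one data set.
3. The untrimmed series as a sensitivity analysis.

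Item 2 is essential. Trimming three steps from the speed series alone would leave squeezes relocated to three steps before the turn in, or at the edge of, deleted data. With a three-step margin the last retained step is the fourth before the turn, one step earlier than the script says, so the analysis text should acknowledge the difference.

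Cost: with a three-step margin, 6 of 40 straight steps per length (15%), a few start-up steps and a little extra scripting. No new data are needed.

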## Task 2: Perceptive accuracy for STS duration variations during repeated STS postural transitions

The participants will be tested on a armless chair of normalized seat height, for their ability to accurately perceive changes in their self-paced sit to stand duration.

They will be instructed to perform STS repetitions at a fixed pace, but to execute each transition from sitting to standing as fast as possible. Sitting with the back rested on the back-support will be the starting position of the test. After the first STS transition (i.e. starting from the first standing position), they will be presented with a countdown of 10 seconds during which they must return to the sitting position and, from that position, perform the following STS transition. The participant will be asked to use the time in between STS repetitions to evaluate their sit-to-stand duration, comparing it with the previous, and decide if to report (or not) a change in STS duration (using the same handheld sensor as during the 6MWT). The STS execution will be stopped by the examiner after 36 repetitions.

Neutral instructions will be provided to the subject before starting the STS test by reading the following script: "When you will hear the beep tone, squeeze the sensor and start performing sit-to-stand repetitions, doing each of them standing up at the maximal speed that you can use to stand up safely. Be aware that we are not asking you to perform as many repetitions you can in a limited amount of time, but that you will be asked to stand up from the chair once every 10 seconds, you just have to do each repetition at your maximal speed: going from sitting to standing as fast as you can. Natural variations in your sit-to-stand speed may occur between repetitions. We want you to notice and, starting from the second repetition, report them using the handheld sensor: if you perceived a change in the time needed to stand up, being it shorter or longer does not matter (you will not have to indicate it), squeeze the sensor in your hand during the resting phase. In between repetitions you will have 10 seconds to decide if to report a change: in the case you didn't notice any change, simply don't squeeze."

Participants will be also equipped with headphones. Using the same set of wearable sensors, as in task 1 (6MWT overground), to detect motor performance will allow us to then confront the time and frequency of the reports with the actual STS duration variations, and propose novel outcome measures: a perceptive threshold for STS duration changes and the ratio between reporting frequency and actual STS duration variability, reflecting perceptive accuracy (see example plot from piloting in Figure 8). The intensity of perceived fatigue and a short structured interview will follow in the same way as in task 1 (6MWT overground).

[figure not shown]

Figure 8 Perceptive accuracy for STS duration variations during repeated STS postural transitions: Task 2 illustration, wearables placement and Perception vs Performance plot graphic illustration.

### Repetition of Task 1 and Task 2 with adapted instructions to quantify perceptive accuracy for the detection of changes in movement quality

The participants will repeat the 2 experimental tasks in the same order, but will be asked to detect changes in their movement quality. The different neutral instructions, modified accordingly to the selected objective parameter of movement quality, will be provided to the subject before starting the 6MWT or the STS repetitions.

In this study the movement quality parameter we will focus on will be the ‘smoothness’ of movements: it will be quantified, with the same wearable sensors configuration as in the previous part, by parameters such as the Harmonic Ratio of gait during Task 1 and the Dynamic Complexity of the STS transition in Task 2, and explained to the participants as ‘a movement that happens in a continual fashion, without any interruptions’.

- Task 1 (6MWT overground) instructions: “When you hear the beep tone, squeeze the sensor and start walking at the maximal speed that you can maintain safely for the 6 minutes-length of the experiment. During this period, but only for the straight parts of the walking track, please pay attention to your walking smoothness. Natural variations in your walking smoothness may occur during the test. We want you to notice and report them using the handheld sensor being them positive or negative: this information does not matter for our test and therefore you will not have to indicate it: as soon as you perceive a change in your walking smoothness, squeeze the sensor in your hand to save your report. Report only changes in smoothness that you perceived during the straight parts of the walking tract, all the variations that are due to the turning will be cut out from the analysis. If you will squeeze during a turn, that report will be saved as if it was given three steps before the turn.”
- Task 2 (STS) instructions: “When you hear the beep tone, squeeze the sensor and start performing STS repetitions, doing each of them standing up at the maximal speed that you can use to stand up safely. Be aware that we are not asking you to perform as many repetitions you can in a limited amount of time, but that you will be asked to stand up from the chair once every 10 seconds, you just have to do each of the STS at your maximal speed: going from sitting to standing as fast as you can. Natural variations in your STS smoothness may occur between STS repetitions. We want you to notice and, starting from the second repetition, report them using the handheld sensor: if you perceived a change in the smoothness of your stand up movement, being it positive or negative does not matter (you will not have to indicate it), squeeze the sensor in your hand during the resting phase. In between repetitions you will have 10 seconds to decide if to report a change; in the case you didn’t notice any change, simply don’t squeeze.”

This will allow us to explore domain specific differences in perceptive accuracy within subjects.

---

